[name]
Chirurgia Generale ed Oncologica
Ospedale Mauriziano "Umberto I", Torino,
Office: [name]
[contact]
e-mail: [contact]

Torino, September 9, 2025

"Resection of the mesentery vs Kono-S anastomosis in preventing surgical recurrence for primary Crohn Disease: the REMEASURE prospective, randomized, controlled trial"

Clinical Trial. Gov number NCT07164209

Remeasure study protocol + statistic

Sincerely

[name]

REsection of the MEsenteric vs Anastomotic configuration and SUrgical REcurrence.

REMEASURE Trial in Crohn's Disease V2.1

Resection of the mesentery with functional end-to-end anastomosis vs Kono-S anastomosis in preventing relapse after ileocolic resection for primary Crohn's Disease.

A prospective, monocentric, randomized trial.

[name]*

* Consultant Surgeon, Division of General and Oncologic Surgery. Department of Surgery.

Ospedale Mauriziano "Umberto I", Torino, Italia.

Office: [name]. [contact]. E-mail: [contact]

Background

Crohn's disease (CD) is an Inflammatory Bowel Disease (IBD), with a relapsing and remitting course, and with an annual incidence of 3–25 per 100000 inhabitants. Over 80% of patients with CD will require a surgical procedure due to abdominal complications within 15 years from diagnosis, and 50% of them will require reoperation for recurrent intestinal disease in the next 15 years^{1,2}.

The gold standard surgical treatment of CD patients, as reported by latest ECCO, ECCO-ESCP, and SICCR guidelines, is based on laparoscopic approach, bowel resection without microscopically disease-free margins, and stapled side-to-side anastomosis³⁻⁵. However, two novelties have recently appeared in the field of CD surgery, both aimed to improve long-term surgical recurrence: the inclusion of the mesentery in the resection of a diseased bowel loop, and a new anastomotic configuration to leave the mesentery far from the anastomotic margins^{6,7}.

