function as a pro-inflammatory agent; adipocytes release molecules like adiponectin and leptin are implicated in the production of pro and anti-inflammatory cytokines. Fibrocytes also play a central role in the development of systemic inflammation. In pathological states involving mesenteric inflammation (including CD) circulating fibrocytes levels are elevated, secreting cytokines, favoring antigen presentation and enhancing the production of metalloproteinases¹². The most evident link between the mesentery and Crohn's disease is the macroscopic phenomenon of "fat wrapping" or "creeping fat," where mesenteric fat is inflamed and extends beyond its normal anatomical distribution over the surface of the contiguous intestine. Fat wrapping is a typical and constant finding in Crohn's disease, and is absent in all other forms of intestinal inflammation. The degree of fat wrapping seems to correlate with the severity of intestinal inflammation in the contiguous intestine. Furthermore, some patient presents with extensive lymph nodes enlargement throughout the mesentery tributary of a diseased segment. The reason of this phenomenon and its pathological rule are nowadays completely unknown. In consideration of the above-mentioned evidences, we could target the CD therapy also on the mesentery. At present there are no drugs specifically designed to act on the mesentery, so that the only target-therapy is surgical removal. Mesenteric division in CD is challenging because of bleeding that may be difficult to control^{7,9,13}. Excision of the mesentery is associated with an increased lymphatic tissue removal; this may reduce the immunological stimulation, resulting in improved post-operative outcomes. It may also reduce the recruitment of fibroblasts which subsequently migrate to the intestinal surface⁸. Coffey et al. reported the first retrospective study demonstrating the clinical relevance of including the mesentery in ileocolic resection for CD. The authors analyzed the rate of surgical recurrence after inclusion of the mesentery during ileocolic resection for CD, by comparing two cohorts of patients: cohort A (30 patients who underwent classical ileocolic resection close to the bowel) and cohort B (34 patients in which the affected mesentery was fully dissected and partially excised). As a result, cumulative reoperation rate for CD recurrence were 40% and 2,9% in cohort A and B respectively. In addition, intestinal length and margin positivity rates were both reduced, while nodal yield was increased, following mesenteric resection⁷.

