
With the same intent of reducing surgical recurrence rate after ileocolic resection of CD, Kono et al. published in 2011 a paper concerning a new technique of an anti-mesenteric, functional end-to-end anastomosis (EEA), called Kono-S anastomosis⁶. After the bowel and the corresponding mesentery have been mobilized, ileal and colonic edges are transected with a linear cutter, with the mesentery

located at the center of the stump; the intervening mesentery is divided close to the bowel, to avoid any devascularization or denervation. The 2 staple lines are approximated to create a kind of supporting column to maintain the anastomosis caliber. Two longitudinal enterotomies, 7 cm long, are made at the antimesenteric side of the 2 bowel stumps, starting from 1 cm from the staple line. A hand-sewn, side-to-side, antimesenteric anastomosis is then performed, approximating the anastomotic ends in a transverse fashion. The endoscopic recurrence rate has been reported to be lower with Kono anastomosis than with conventional EEA, and two studies showed a 5-year surgical anastomotic recurrence rate was 1.8%, during a median follow-up of 65 months (range, 43–138 months)^{14,15}. Shimada et al. published in 2019 a retrospective trial showing that the Kono anastomosis was associated with a low risk of recurrence after 1 year. Kono anastomosis was reported to be superior in terms of anastomotic recurrence at 5 years, using Kaplan–Meyer analysis, as well as having a lower anastomotic leakage rate¹⁶. The first RCT comparing Kono-S anastomosis and standard anastomosis in CD has been recently published. The authors found a significant reduction in postoperative endoscopic recurrence rate, and also a decrease in the severity of endoscopic recurrence score, in favor of the Kono-S technique comparing to a conventional side-to-side anastomosis, performed with a double fire of a linear stapler, and with the transverse staple line buried in a running suture¹⁵. Despite some peculiarities in terms of suturing, the Kono anastomosis is a functional, end- to-end anastomosis which keeps the mesentery distant from the mucosal sutures but leaving in situ the mesentery regardless of its characteristics. In the study by Luglio et al., it was compared with a standard side-to-side anastomosis, but without mesentery removal¹⁵.

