Patients who meet inclusion criteria will be randomized between two surgical procedures:

The excision of the mesentery and ileocolic anastomosis (group A) and the Kono-S anastomosis (group B) after ileocolic or ileo-cecal resection. The operation could be performed with open or laparoscopic approach. Two videos will be provided showing the anastomotic techniques in order to improve standardization among the contributing Centers.

- 1) Excision of the mesentery: the mesentery is fully dissected and excised to the limit of macroscopic “fat wrapping”, where mesenteric fat is inflamed and extends beyond its normal anatomical distribution over the surface of the contiguous intestine. A functional, end-to-end, stapled anastomosis between colon and ileum is than performed (the functional end-to-end is a latero-lateral, antiperistaltic, antimesenteric anastomosis, which has a similar, final configuration of the Kono-S).
- 2) Kono-S anastomosis: the mesentery is not removed but cutted close to the bowel. The bowel is then divided transversely by placing a linear stapler perpendicular to the intestinal lumen and the mesentery. The corners of the two staple lines are reinforced and the two stumps are approximated using 5–7 sutures to create the column. If the caliber of the two intestinal segments differs significantly, the sutures should be spaced to evenly distribute the surplus tissue of the larger segment, in order to achieve good approximation and stable support for the anastomosis. To create the anastomosis, an antimesenteric longitudinal enterotomy (or colostomy) is performed on each stump to allow a transverse lumen of 7 cm in diameter for the small bowel or closer to 8 cm for the colon. In this way the supporting column is located immediately behind the posterior wall of the anastomosis providing a rigid and stable support to prevent mechanical deformation and functional constriction of the lumen of the anastomosis.

Study Design for a Randomized Trial

The aim of the study is to determine whether the two therapies have the same efficacy; therefore, we are in the framework of No Difference Testing.^{17 18}

Based on previous literature the expected reduction rate of 6 months for endoscopic recurrence after Kono anastomosis was 25% in order to be more conservative (45% after resection of the mesentery group and 20% in the Kono group), and a value of 0.05 (1-sided) and 75% power was estimated a sample size of 70 patients.

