After enrollment, patients will be randomly assigned in a 1 : 1 ratio between Kono anastomosis and resection of the mesentery, by controlling for age, sex, smoking habits, and other health related quantities, including the origin from different centers will be taken into account.

The two Groups will be compared for safety in terms of perioperative characteristics and postoperative complications. Continuous variables will be analysed using a two-tailed, unpaired, Student's t-test, and proportions will be compared using two-tailed, Fisher's exact or chi-square test, where appropriate. Since multiple tests will be performed, a suitable p-value correction will be used, such as Bonferroni correction. A model-based approach for the multivariate analysis, setting the presence of postoperative complications as dependent variable will be performed, a binary logistic regression will be used, with all the variables significant at the univariate level as predictors.

The greatest emphasis will be on the dummy variable encoding the different treatments (for example 1 = "Kono anastomosis", 0 = "Resection of the mesentery"). In this context, the equivalence may be evaluated in two ways: 1 • the associated coefficient of the regression is not significant from a statistical point view. • the Odds Ratio (OR) associated to the corresponding coefficient is close to 1 (and in particular the 95% confidence interval contains 1), meaning that changing the type of treatment does not affect the probability postoperative complications.

Endoscopic, clinical, and surgical recurrences will be analyzed using the time-to-event estimates of the Kaplan-Meier function, and compared for univariate analysis with the Log-rank test. Cox proportional hazard regression analysis will be used to set up a predictive model simultaneously exploring the effects of the independent variables on recurrences in relation to time. Significance will be considered for p-value inferior to 0.05.

Data collection

Data will prospectively be collected using a web-based, dedicated, REDCup database. A local study manager will be identified for each participating center, and a dedicated REDCup username and password will be assigned. The completeness and congruity of the data will be checked periodically by the study's Scientific Committee. The Scientific Committee will refer to the local managers for any request for clarification.

Duration of the study

24 months

Ethical consideration

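### The multivariable Cox model is planned for recurrences without excepting surgical recurrence, for which the protocol's own rates imply about 1.6 events in 70 patients

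*Protocol*

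**What the plan says.** The Endpoints section lists surgical recurrence after 24 months as a secondary endpoint; the primary endpoint is endoscopic recurrence at 6 months. The analysis text under Study Design for a Randomized Trial treats the three kinds of recurrence together: "Endoscopic, clinical, and surgical recurrences will be analyzed using the time-to-event estimates of the Kaplan-Meier function", with a log-rank comparison. It continues: "Cox proportional hazard regression analysis will be used to set up a predictive model simultaneously exploring the effects of the independent variables on recurrences". Surgical recurrence is not excepted from either step.

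The trial is sized only on the primary endpoint, from "45% after resection of the mesentery group and 20% in the Kono group", with "a value of 0.05 (1-sided) and 75% power was estimated a sample size of 70 patients". Allocation is 1:1.

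Two surgical recurrence rates in the Background correspond to the trial arms. For Kono-S, "two studies showed a 5-year surgical anastomotic recurrence rate was 1.8" per cent. For mesenteric excision, a retrospective comparison reports "40% and 2,9% in cohort A and B respectively". Cohort B (34 patients) had the mesentery excised; cohort A had conventional resection, which is not a trial arm. The Background also gives a figure for Crohn's disease surgery in general: half of operated patients need reoperation over the following 15 years.

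**The concern.** A Cox model draws its information from events, not from patients. If surgical recurrence is as rare after both procedures as the Background suggests, there may be no event, one or two in the whole trial. When all events fall in one arm, the partial likelihood has no finite maximum for the treatment term, and software returns a hazard ratio drifting to zero or infinity with a meaningless standard error. Adding covariates makes this more likely.

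At stake is a secondary analysis that would either fail or yield uninterpretable estimates. There is also a risk of misreading. The section frames the whole trial as a test of no difference between the procedures, and with one or two events a non-significant result is close to certain whatever the truth. Such a result says almost nothing about whether the procedures prevent reoperation equally well.

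**Working it through.** **The plan's own figure.** The unpooled two-proportion formula with one-sided alpha 0.05 and 75% power gives, per arm, (1.645 + 0.674)² × (0.45 × 0.55 + 0.20 × 0.80) / 0.25² = 5.379 × 0.4075 / 0.0625 = 35.07. This reproduces 70 in total. The 1:1 ratio then gives 35 per arm (no losses assumed). The protocol states no expected number of surgical recurrences.

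**Expected events, quoted rates applied in full at 24 months.**
- Kono-S: 35 × 0.018 = 0.63.
- Mesenteric excision: 35 × 0.029 = 1.02.
- Total: 1.65.

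**Chance of an empty arm.**
- No event after Kono-S: 0.982³⁵ = 0.53.
- No event after mesenteric excision: 0.971³⁵ = 0.36.
- At least one arm empty: 1 − (1 − 0.53)(1 − 0.36) = 0.70.
- From the sum of the two binomial counts: no event at all 19%, at most one 51%, at most two 77%, five or more about 2%.

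**Other readings of the rates.** Scaling assumes a constant hazard. A finite Cox estimate was checked in 2,000 simulated trials per row, for treatment alone and for treatment, sex, smoking and age (covariate distributions assumed, no covariate effects, no dropout).

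| Rates at 24 months | Expected events | An arm empty | Finite, treatment only | Finite, four terms |
|---|---|---|---|---|
| 1.8% and 2.9% in full | 1.65 | 70% | 31% | 14% |
| Kono-S scaled from 5 to 2 years (0.72%), 2.9% in full | 1.27 | 86% | 12% | 5% |
| Both scaled, 2.9% assumed to be a 5-year figure (0.72%, 1.17%) | 0.66 | 92% | 9% | 3% |
| Generic 50% over 15 years in both arms: 1 − 0.5^(2/15) = 8.8% | 6.2 | 8% | 92% | 78% |

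In the last row the model usually converges, but on 6.2 / 4 ≈ 1.5 events per term, with 13% power for a hazard ratio of 2 (Schoenfeld formula). By the same formula, a hazard ratio of 0.5 at 80% power needs 66 events.

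**What the log-rank test can show.** With 35 per arm and all events in one arm:
- Two events: observed minus expected = 2 − (35/70 + 34/69) = 1.007, variance 0.500, chi-square 2.03, p about 0.15.
- Four events: 4 − (35/70 + 34/69 + 33/68 + 32/67) = 2.044, variance 0.999, chi-square 4.18, p = 0.041.

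So at least four events, all on one side, are needed for p < 0.05.

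**What the counts alone would show.** For 0/35 the exact two-sided 95% upper limit is 1 − 0.025^(1/35) = 10%; for 1/35 it is about 15%. An arm without events is still compatible with a recurrence risk well above either quoted rate.

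**The case against.** The event rate is insecure. The 2.9% is one patient of 34 in a retrospective cohort, with an exact 95% interval of about 0.1% to 15%; the upper end would give about 5 events in that arm alone. The protocol gives no follow-up time for it. The 1.8% counts anastomotic recurrence only, while the endpoint is surgical recurrence without that limit. Under the generic 15-year figure the model would usually converge. All of this stands, and it means that failure to converge is likely on the arm-specific rates but not certain. It does not rescue the model, because 5 or 6 events still cannot carry several covariates.

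It can also be said that covariate lists, event minimums and fallbacks belong in a statistical analysis plan, which is not shown. That is fair, and their absence is not the point. The point is that the protocol names a method and applies it to an outcome that cannot support it.

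Four stronger readings are tempting and are not supported:
- A reader might infer that the protocol would declare equal efficacy on surgical recurrence from a non-significant result. The explicit rule to that effect is written for the logistic model of postoperative complications; the recurrence paragraph has no such rule. The general no-difference framing makes the extension possible, but it is not stated.
- A reader might infer that the Kaplan-Meier and log-rank analyses fail too. Both can be computed with an empty arm. The log-rank test is merely very weak here and its p-value approximate.
- A reader might extend the point to endoscopic recurrence. The sizing rates give 35 × 0.45 + 35 × 0.20 = 22.75 events, enough for a small model.
- The cover title's phrase "in preventing surgical recurrence for primary Crohn Disease" might suggest that this is the main outcome. The stated aim and primary endpoint are endoscopic.

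**Conclusion.** The point holds for the multivariable Cox model of surgical recurrence, and only for that. On the protocol's arm-specific rates, applied in full, about 1.6 events are expected. The treatment hazard ratio has no finite estimate in about 70% of trials, and a four-term model has none in about 86%. On the most generous generic rate in the protocol the model would usually converge but would rest on about 1.5 events per term.

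The assumptions are 35 patients per arm, no losses, and 24-month rates no higher than those quoted; the scaled and generic rows also assume a constant hazard, and the four-term result uses assumed covariates. Losses would lower the counts further, as would accrual within the stated 24-month study duration. The sample size and the primary endpoint are unaffected. This is a modest correction to a secondary analysis.

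**What to change.** In Study Design for a Randomized Trial, except surgical recurrence from the Cox model and state instead:
- Surgical recurrence at 24 months will be reported as the number of events per arm and the risk difference with an exact 95% confidence interval.
- Kaplan-Meier curves may be shown, and any log-rank p-value is descriptive.
- A non-significant result will not be read as equal efficacy on this endpoint.

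The last sentence is worth adding because of the trial's no-difference framing, even though the existing non-significance rule concerns postoperative complications.

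The cost is a change of wording, with no extra patients, visits or data. What is given up is a secondary model that could not have been fitted reliably.
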